7.3 Treatment Plan for AZD1775 single agent (Arm C)

7.31 Safety Portion

The Safety portion of this trial will treat and monitor up to six patients in the arm and observe them for a minimum of 28 days to assess toxicities.

Starting Dose: Single Agent

Agent	Dose	Route	Day(s)	ReRx
AZD1775	200 mg	PO daily	1-5, 8-12, 15-19,	Every 28 days ¹
			22-26 ²	

¹Cycle length can be increased to 6-8 weeks

²AZD1775 should be taken either 2 hours before or 2 hours after a meal. Note: if the starting dose is not tolerated, a lower dosing cohort will be explored and follow the recommendation as outlined in Section 8.1 Table 8.12.

7.32 Expansion Portion

The Expansion portion of this trial will commence for Arm C as soon as the Safety Portion is completed.

C .	. •	D
N'tor	ting	1 logo
- NIAL	IIII9	LINSE
Diai		

Agent	Dose	Route	Day(s)	ReRx
AZD1775	MTD	PO daily	1-5, 8-12, 15-19,	Every 28 days ¹
			22-26-	

¹Cycle length can be increased to 6-8 weeks

²AZD1775 should be taken either 2 hours before or 2 hours after a meal.

7.4 Toxicity Assessment for Safety Portion (first 6 patients on each Arm)

Toxicity will be measured per NCI-CTCAE version 4. DLT is defined as an adverse event occurring during the first cycle of treatment that is not clearly related to the patient's underlying disease and that meets one of the following:

- Grade 3 AST, ALT or alkaline phosphatase will be considered dose limiting on an individual basis or if lasts more than 5 days
- Grade 3 as per NCI Common Terminology Criteria for Adverse Events (CTCAE) version 4.0 that does not resolve to ≤ Grade 2 within 7 days
- Grade 4 as per NCI Common Terminology Criteria for Adverse Events (CTCAE) version 4.0

NOTE: Myelosuppression will not be considered in evaluating toxicity in patients with acute leukemias or similar advanced myeloid malignancies

(MDS) except where bone marrow (BM) hypoplasia occurs for >52 days with BM cellularity <5% in the absence of residual leukemia/disease.

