4.0 Test Schedule

Table 4.1: Test Schedule for Elderly Newly Diagnosed and Relapsed/Refractory AML patients

23

	Active Monitoring Phase					
Tests and procedures	≤14 days prior to registration	≤7 days prior to registration	Cycle 1 Days 1, 8, 15, & 28(+3 days) ^{5, 13}	Cycles 2 & 3 Days 1, 15, and 28 (+ 3 days) ^{5, 13}	Cycles 4+Day 1 and Beyond(+/-3 days) ^{5, 17}	EOS ²
History and exam, wt, PS, vitals	X		Х	X ¹³	X ¹³	Х
Height	Х					
Adverse event assessment	Х		Х	Х	X	Х
Hematology group WBC ANC Hgb PLT		X	х	х	X ⁹	х
Chemistry group: sodium, potassium, calcium, creatinine, bicarbonate, glucose, chloride, albumin, BUN, alkaline phosphatase, AST, ALT, total protein, total bilirubin, LDH		X	X	Х	Х	Х
TLS monitoring (for selected AML patients): BUN, calcium, CO2, chloride, creatinine, glucose, potassium, sodium, uric acid, phosphorus			X ¹⁴	X ¹⁴		

PT/PTT and D-dimer			X ¹⁹			
Serum pregnancy test ¹		Х				
Bone marrow biopsy and						
aspirate procedure	\mathbf{v}^{11}		\mathbf{v}^3	\mathbf{v}^3	\mathbf{v}^3	\mathbf{V}^{10}
(cytogenetics or FISH) ¹⁵	Λ		Λ	A	Λ	Λ
Bone marrow aspirate						
research specimens	X^8		X^7	\mathbf{X}^7	\mathbf{X}^7	X ⁶
(see Section 14.0) ^R						
Blood specimens (see	1.0					
Section $(14.0)^{R}$	X ^{4, 8}		X^4	X^4	X^4	X^4
Buccal swab (optional,	x					
see Section 14.0) ^K	 					
Patient Questionnaire	v		\mathbf{V}^{16}	V^{16}	V^{16}	\mathbf{V}^{16}
Booklet ¹²	Λ		Λ	Δ	Δ	Δ
ECG $(12 \text{ lead})^{18}$		X				X

1. For women of childbearing potential only.

2. 30 days (+/-3days) post last dose of study drug

3. For AML patients: marrow aspirates and biopsies will be done after cycle 1 (at physician's discretion), after cycles 2 and 4, and then at physician discretion). In addition, bone marrow should be performed at time of suspected CR/CRi and/or disease progression and at physician discretion as clinically indicated. Note: Bone Marrow Aspirate and biopsy may be avoided aftercycle 4 as determined by study chair or treating physician (i.e. if determined to not yield information that would change clinical management).

4. Blood specimens for research sampling to be collected as defined in Section 14.

5. Day 1 assessments do not need to be repeated if pre-registration or Day 28 assessments completed within 48 hours of Day 1.

6. Only if an EOS marrow sample is collected as part of standard of care

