- 15. Either conventional cytogenetics or FISH panel (or both based on physician discretion) for AML to be performed at baseline. If diploid cytogenetics at baseline, subsequent cytogenetic studies may be omitted unless disease progression is suspected. For FISH based cytogenetic assessments, an entire AML FISH panel should be performed at baseline, while on subsequent marrows only positive specific FISH abnormalities/probes need to be repeated unless disease progression is suspected, in which case a full AML FISH panel or instead conventional cytogenetics should be performed.
- 16. Booklets to be completed at end of all cycles.
- 17. Prior to the start of treatment.
- 18. ECG to be repeated if cardiac symptoms occur or as otherwise defined in the test schedule.
- 19. To be tested on C1D1 prior to treatment.
- R Research funded (see Section 19.0).

Table 4.2: Test Schedule for HMA failure MDS patients

			Active Monitoring Phase			
Tests and procedures	≤14 days prior to registration	≤7 days prior to registration	Cycles 1 Days 1, 8, 15, & 28(+3 days) ¹²	Cycle 2 Days 1, 15, and 28 (+ 3 days) ^{10, 12}	Cycles 3+ Day 1 and Beyond(+/-3 days) ^{10, 12}	EOS ²
History and exam, wt, PS, vitals	Х		X	Х	Х	Х
Height	Х					
Adverse event assessment	X		Х	Х	X	Х
Hematology group WBC ANC Hgb PLT		х	х	Х	Х	х
Chemistry group: sodium, potassium, calcium, creatinine, bicarbonate, glucose, chloride, albumin, BUN, alkaline phosphatase, AST, ALT, total protein, total bilirubin, LDH		X	X	Х	Х	X
Serum Erythropoietin level	Х					
Serum pregnancy test ¹		Х				
Bone marrow biopsy and aspirate procedure (cytogenetics or FISH ⁹)	X ⁶			X ³	X ³	X ⁷
Blood specimens (see Section 14.0) ^R	X ⁴		X^4	X^4	X^4	X^4
Buccal swab (see Section	Х					

14.0) ^R						
Bone marrow aspirate						
research specimens	X^6			X^5	X^5	X^5
(see Section 14.0) ^R						
Patient Questionnaire	\mathbf{v}		\mathbf{v}^{8}	\mathbf{v}^8	\mathbf{v}^8	v
Booklet ⁸	Λ		Λ	Λ	Λ	Λ
ECG $(12 \text{ lead})^{11}$		Х				Х

1. For women of childbearing potential only

2. 30 days (+/-3days) post last dose of study drug

3. Marrow biopsies only to be done at End of cycle 2, End of cycle 4, at time of suspected CR/CRi and thereafter at physician discretion as clinically indicated (i.e. disease progression).

4. Blood specimens for research sampling to be collected as defined in Section 14.

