7.2 Treatment Plan for AZD1775 combined with AraC (Arms A and B)

7.21 Safety Portion

The Safety portion of this trial will treat and monitor six patients in each arm and observe them for a minimum of 28 days to assess toxicities.

Starting Doses: Multiple Agent

Agent	Dose	Route	Day(s)	ReRx
AraC ¹	20 mg	SC twice daily ²	$1-5 \& 8-12^3$	Every 28 days ⁴
AZD1775	200 mg	PO daily	$1-5\& 8-12^3$	Every 28 days ⁴

¹ Starting dose of a fixed dose of 20 mg s.c. per a single dose twice daily. In individual cases, a 10 mg/m^2 not to exceed 20 mg can be used alternatively.

²SC administration preferred

³ AZD1775 should be taken either 2 hours before or 2 hours after a meal. A day 1-10 dosing schedule will be permitted as an alternative, in which case AZD1775 should be given days 1-10 as well.

⁴Cycle length can be increased to 6 and maximally 8 weeks

Note: if the starting dose is not tolerated, lower dosing cohort combination will be explored and follow the recommendation as outlined in Section 8.1 Table 8.11.

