16.3 Sample Size, Accrual Rate, and Study Duration

This design is expected to accrue 18 patients to the safety portion with the possibility of enrolling up to 54. Six patients in each of the safety arms will be treated at the MTD and thus will be eligible for primary endpoint analysis. An additional 15 patients in Arm A and 14 patients in both arm B and C will be enrolled per treatment arm in the expansion portion with the addition of another 2 per arm to account for ineligibility, cancellation, major treatment violation, or other reasons. Thus the final accrual may be as large as 102 or as low as 67 (Arm A: 23; Arm B: 22; Arm C: 22).

The anticipated accrual rate is 4-6 evaluable patients per month. Therefore, the accrual period is expected to be approximately 1.5-2 years. The primary endpoint will be evaluated approximately 2.5 years after the trial opens, or after the last patient accrued has been observed for at least 4 months. The total study duration is expected to be approximately 2.5 years.

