16.4 Secondary Endpoints

- 16.41 Safety and tolerability data will be compiled. The maximum grade for each type of adverse event will be recorded for each patient, and frequency tables will be reviewed to determine patterns (by arm, disease and overall). Additionally, the relationship of the adverse event(s) to the study treatment will be taken into consideration. The rate of grade 3 or higher non-hematologic adverse events, and the rate of grade 4 or higher adverse event (hematologic and non-hematologic) will be computed each with a 95% exact binomial confidence interval.
- 16.42 Summary statistics for clinical benefit (mean and standard deviations for continuous variables and frequencies and percentages for discrete variables) will be compiled for hematologic improvements and transfusion requirements.

- 16.43 Duration of response is defined for all evaluable patients who have achieved a response as the date at which the patient's earliest best objective status is first noted to be a CR/CRi response to the earliest date progression is documented. If a patient dies subsequent to the response without a documentation of disease progression, the patient will be censored at the last date disease was assessed. In the case of a patient failing to return for evaluations before a documentation of disease progression, the patient will be censored for progression on the date of last evaluation. The distribution of duration of response will be estimated using the method of Kaplan-Meier (1958).
- 16.44 Time to response/progression is defined as the time from registration to the earliest date of documentation of response/disease progression. If a patient dies without a documentation of disease progression the patient will censored at the last date disease was assessed. In the case of a patient starting treatment and then never returning for any evaluations, the patient will be censored for progression 1 day post-registration. The distribution of time to progression will be estimated using the method of Kaplan-Meier (1958).
- 16.45 Survival time is defined as the time from registration to death due to any cause. The distribution of survival time will be estimated using the method of Kaplan-Meier (1958).
- 16.46 Time to AML or death is defined for all evaluable patients with MDS as the time from registration to leukemic transformation or death due to any cause. The distribution of time to AML or death will be estimated using the method of Kaplan-Meier (1958).

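### The run-in dose rules need correcting in three places: a marrow DLT longer than the usual first cycle, a Grade 4 criterion that leaves out Grade 5, and two conflicting dose algorithms (7.4, 7.7, 16.7)

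*Combined protocol and SAP*

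**What the plan says.** **DLT definition (7.4).** The window is the first cycle: "DLT is defined as an adverse event occurring during the first cycle of treatment", provided the event is not clearly due to the disease. Myelosuppression does not count, "except where bone marrow (BM) hypoplasia occurs for >52 days with BM cellularity <5% in the absence of residual leukemia/disease". One of the qualifying criteria reads "Grade 4 as per NCI Common Terminology Criteria for Adverse Events (CTCAE) version 4.0", with nothing about higher grades.

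**Observation.** The cycle is 28 days and may be extended to 6 weeks and at most 8 (7.21, footnote 4). The run-in is to treat six patients per arm and "observe them for a minimum of 28 days to assess toxicities". Sections 7.71 and 16.7 both require observation for one cycle.

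**Marrow schedule (4.0).** In AML, a marrow after cycle 1 is at the physician's discretion, with further marrows "after cycles 2 and 4, and then at physician discretion". In MDS: "Marrow biopsies only to be done at End of cycle 2, End of cycle 4", or when CR/CRi is suspected.

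**Grade wording elsewhere.** Section 16.41 reports "the rate of grade 4 or higher adverse event (hematologic and non-hematologic", and the stopping rule in 16.82 also covers grade 4 or higher.

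**Dose algorithms.** Section 7.7 treats three patients, pauses, steps down on two or more DLTs in three, and otherwise adds three more. At two or more in six, the MTD becomes the previous dose, unless only three patients were treated there. Section 16.7 looks once after six, steps down at two or more, and treats another six. It refers to a DLT definition that is said to follow but does not.

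**The concern.** The run-in fixes the dose for 43 planned evaluable expansion patients (15 + 14 + 14, section 16.3), so what enters the 2-of-6 count matters.

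1. The only marrow event that can be a DLT takes longer than the usual cycle in which DLTs must occur. Section 7.4 does not say whether onset in cycle 1 is enough, or whether the 52 days run from day 1 or from onset. If onset is enough, the six-patient decision can still be taken before the criterion can be met in patients who enrolled late.
2. Without Grade 5, a fatal toxicity with no earlier qualifying event is literally not a DLT. Sections 7.75 and 13.4 then treat the patient as uninformative and add another.
3. With two DLTs in the first three patients, 7.72 steps down at once. Section 16.7 has no look at that point, so following it alone means treating three more at a level that has already failed. The previous-dose wording belongs to an escalation design. This trial starts at its top level and only steps down, so that wording could literally name a level at which nobody has been treated.

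**Working it through.** **The plan's own figures.** Section 16.3 expects 18 run-in patients and allows up to 54. These equal 3 arms x 6 = 18 and 3 arms x 3 dose levels x 6 = 54. Both fit a rule of six patients per accepted level. The plan gives no operating characteristics for the run-in, so the rest is computed here.

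**Cycle length against the marrow criterion.** A standard cycle is 28 days, a 6-week cycle 42 and an 8-week cycle 56. Only the last exceeds 52. More than 52 days is first reached on day 53 for onset on day 1 (25 days after day 28), and on day 64 for onset on day 12 (36 days after day 28).

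**Follow-up at the six-patient decision.** Section 16.3 states: "The anticipated accrual rate is 4-6 evaluable patients per month". Assume an even split over three arms, even spacing, 30.4 days per month, 28-day cycles and the pause in 7.71-7.72. The entry gap within an arm is 30.4/(rate/3), which is 15.2 days at 6 per month and 22.8 at 4 per month. The fourth patient enters 28 days after the third, and the decision falls 28 days after the sixth enters.

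| Accrual | Follow-up of patients 1 to 6 (days) |
|---|---|
| 6 per month | 117, 102, 86, 58, 43, 28 |
| 4 per month | 147, 124, 102, 74, 51, 28 |

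The last two patients are short of day 53 in both cases. If the last three enter together after the pause, all three are short.

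**Baseline acceptance.** A level is accepted if at most 1 of 6 has a DLT: (1-p)^6 + 6p(1-p)^5. For p = 0.20, 0.30 and 0.50 this is 0.655, 0.420 and 0.109.

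**Part 3: 7.7 against 16.7.** Under 7.7, acceptance is b0(b0 + b1) + b1 b0, where b0 and b1 are the Binomial(3, p) probabilities of 0 and 1 DLT. At p = 0.30: 0.343 x (0.343 + 0.441) + 0.441 x 0.343 = 0.420. The two rules agree at every p, because two DLTs in three already means at least two in six. The probability that 7.72 stops after three is 0.104, 0.216 and 0.500 at 20%, 30% and 50%. If that look is skipped, the expected excess is three times this: 0.31, 0.65 and 1.50 patients.

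**Part 1: hypoplasia uncountable in the last k patients.** Let the total DLT rate be t, with d of it hypoplasia. Then 6-k patients have rate t and k have rate t-d. Both t and d are assumptions.

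| t | d | k = 2 | k = 3 | k = 6 (never counted) |
|---|---|---|---|---|
| 0.30 | 0.01 | 0.427 | 0.431 | 0.442 |
| 0.30 | 0.05 | 0.457 | 0.475 | 0.534 |
| 0.30 | 0.10 | 0.494 | 0.533 | 0.655 |
| 0.20 | 0.01 | 0.664 | 0.668 | 0.680 |
| 0.20 | 0.05 | 0.696 | 0.717 | 0.776 |
| 0.20 | 0.10 | 0.737 | 0.778 | 0.886 |

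**Part 2: toxic deaths replaced.** If a share d of the DLT rate is deaths that are replaced, the rate among counted patients is p' = (t-d)/(1-d). At t = 0.30:
- d = 0.01: p' = 0.29/0.99 = 0.293, acceptance 0.436
- d = 0.05: p' = 0.25/0.95 = 0.263, acceptance 0.503
- d = 0.10: p' = 0.20/0.90 = 0.222, acceptance 0.601

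If half of the deaths had an earlier qualifying event, d is halved: 0.460 for d = 0.05 and 0.503 for d = 0.10.

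**The case against.** **Marrow criterion.** A reader might infer that this DLT can never be met. The documents do not support that. Cycles may run to 56 days, and a patient with prolonged aplasia is a natural candidate for extension. Reading the first-cycle limit as referring to onset also removes the conflict in definition. In addition, 7.22 holds expansion of Arms A and B until both safety portions are complete, so whichever finishes first gains follow-up. What stands is that extension is permitted but not required, since 8.2 does not demand count recovery, and 7.4 does not state the onset reading.

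**Grade 5.** A reader might infer that a toxic death would be overlooked. It would not. Section 13.4 keeps all toxicity information in the analysis, 10.52 requires 24-hour reporting, 16.82 covers grade 4 or higher, and the team may suspend accrual before a boundary is crossed. The literal reading is surely unintended, and many deaths would follow an event that already qualifies. However, none of these provisions enters the 2-of-6 count, and one death does not trigger a rule that needs three in the first ten patients.

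**Two algorithms.** They can be read together, with 7.7 staging the enrolment and 16.7 giving the six-patient rule. Section 16.3 expects six patients at the MTD, which shows that an untested MTD is not intended. That is fair, and it is why this part concerns exposure and clarity only.

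**Size.** No document gives a DLT rate for this population or a share for hypoplasia or toxic death. Section 1.41 reports no DLTs on monotherapy and rates below 30% at the combination MTDs, in solid tumours. The marrow criterion is narrow, and a share of 1 to 2 points affecting the last two patients moves acceptance by only about 1 to 2 percentage points. This objection stands in full.

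**Conclusion.** The run-in rules are wrong as written in three places, and each should be corrected.

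- **Marrow DLT.** It cannot be completed in a 28- or 42-day cycle, and the dose decision may come before it can be observed. At an assumed 30% DLT rate with 1 to 10 points of hypoplasia uncounted in the last two patients, acceptance rises from 0.42 to 0.43-0.49. The larger k = 6 figures need the strict reading that hypoplasia completed after cycle 1 never counts; the text does not compel it.
- **Grade 5.** On the same assumed range, acceptance rises from 0.42 to 0.44-0.60 if no death had an earlier qualifying event, and by less if some did.
- **Algorithms.** The chance of accepting a level is identical under 7.7 and 16.7. The effect is at most three extra patients per failed level, and only if the look after three is not applied.

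The defects in the text do not depend on the assumed shares; the sizes of the first two effects do. No efficacy sample size, significance level or power is affected.

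**What to change.** 1. **7.4, marrow.** State that hypoplasia with onset in cycle 1 is a DLT once it exceeds the stated duration, even if cycle 2 has begun, and say whether the duration runs from day 1 or from onset. If a case confirmed later brings a level to two or more DLTs in six, re-apply 7.73 to that level. Confirm with blood counts and marrows that are scheduled or clinically indicated; a single end-of-cycle-2 marrow cannot by itself show more than 52 days.
2. **7.4, grade.** Write Grade 4 or higher. Sections 7.75 and 13.4 need no change, because they already exempt DLTs from replacement.
3. **7.7 and 16.7.** Use one algorithm in both: look after three, step down on two or more DLTs, and require six patients with at most one DLT before a level is called the MTD. Delete the escalation wording and refer 16.7 to 7.4 for the definition.

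**Cost.** Items 2 and 3 are wording only. Item 1 adds a decision step, because a level already cleared could be reopened. It needs no extra mandated procedures and no change in sample size. Holding the expansion while a case is pending is optional. For a patient seen for 28 days, the wait is about 25 days (onset day 1) to 36 days (onset day 12). It can be longer if cycles are extended: the end-of-cycle-2 marrow falls near day 56 on 28-day cycles, but at days 84 to 112 on cycles of 6 to 8 weeks.

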7.7 MTD Determination

This MTD determination applies to the Safety Portion. MTD for the safety portion will be defined as the dose level below the lowest dose that induces dose-limiting toxicity in at least one-third of patients (at least 2 of a maximum of 6 new patients).

- 7.71 Three patients will be treated at a given dose level combination and observed for one cycle to assess toxicity (accrual will be suspended while the 3 patients are treated and observed).
- 7.72 If DLT is not seen in any of the 3 patients or in 1 of 3 patients, 3 new patients will be accrued. and treated at the same dose level (accrual will be suspended while the 3 patients are treated and observed). If DLT is seen in 2 or 3 of 3 patients treated at a given dose level, then the next 3 patients will be treated at the next lower dose level, if only 3 patients were enrolled and treated at this lower dose level.
- 7.73After enrolling 6 patients on a specific dose level, if DLT is observed in 1 or less patients, then the combination dose will be considered safe for the expansion phase. If DLT is observed in at least 2 of 6 patients, then the MTD will have been exceeded and defined as the previous dose unless only 3 patients were treated at the lower dose level. In that case, 3 additional patients will be treated at this lower dose level.
- 7.75 If a patient fails to complete one cycle of treatment for reasons other than doselimiting toxicity defined adverse events, the patient will be regarded as noninformative for estimating the MTD and an additional patient will be treated at the current dose level.
- 7.8 Dose escalation will not be allowed for a patient.

7.9a For this protocol, the patient must return to the consenting institution for evaluation at least once every 28 days.

7.9b Local Medical Doctor (LMD) When it has been determined that a patient's malignant disease is stable or objective tumor regression has been observed and the patient is tolerating therapy without excessive toxicity, the drug(s) may be administered by the patient's Local Medical Doctor (LMD). The registering physician retains responsibility for the patient.

In this case, a written statement outlining drug dosage, method of administration, followup tests required, and telephone number to call to discuss any questions with the responsible investigator must be sent with the patient to provide necessary information to the LMD. The LMD will be required to supervise the administration of the study drugs as stipulated in the protocol and provide written documentation that the drug was administered. **8.0 Dosage Modification Based on Adverse Events -** If multiple adverse events are seen, administer dose based on greatest reduction required for any single adverse event observed. Dose modifications apply to the treatment given in the preceding cycle and are based on adverse events observed since the prior dose. Dose modification recommendations listed below are general guidelines, and appropriate dose adjustments for patient safety should be done if needed per treating physician discretion.

ALERT: ADR reporting may be required for some adverse events. See Section 10.0.

